- 3.3. **Sample Size and accrual rate.** It is estimated that 2 patients will be entered into the treatment study each month, therefore, we anticipate 24 months for completion of the study that will require **n=44** total patients for the treatment arm. We are planning to enroll **n=20** patients for “external control patients”. We anticipate 0.5 patients/month for “external control” subjects and accrual will happen concomitant to treatment arm patients. Therefore a total of **64** subjects will be accrued in total including treatment arm and external control.
- 3.4. **Patient Follow up.** Patients will be evaluated weekly from day of transplant until day 100 to measure acute GVHD using standard scoring system (defined in Appendix A). Stage of GVHD will be assessed for each site of involvement (e.g. skin, liver, and gut), as well as a composite score for overall acute GVHD grade determined. Pathologic confirmation of aGVHD will be dictated by usual clinical practice. Patient will be followed on days +90 +/-14, 120 +/- 14, 150 +/- 14, 180+/- 14, 270+/-30, and 360 +/- 30 for chronic-GVHD assessment and adverse events toxicity assessment. Taper of immunosuppression is suggested- not mandatory and treatment of GVHD is not mandated (section 6.2-6.3).
- 3.5. **Withdrawal.** from the study will take place under the following circumstances: those patients who sign consent for the study, but fail to initiate treatment due to:
- 3.5.1. denial of coverage from insurance provider
 - 3.5.2. disease progression prior to initiation of treatment
 - 3.5.3. death prior to initiation of treatment
 - 3.5.4. withdrawal of patient consent at any time after therapy

4. Patient Population: Inclusion and Exclusion criteria

- 4.1. **Inclusion Criteria:**
- 4.1.1. Male or female

- 4.1.2. Age \geq 18 years or older at time of enrollment
 - 4.1.3. Signed informed consent
 - 4.1.4. Hematologic disorder requiring allogeneic hematopoietic cell transplantation
 - 4.1.5. LVEF \geq 45% by MUGA scan or echocardiogram
 - 4.1.6. FEV1, FVC, and DLCO adjusted \geq 50% of predicted values on pulmonary function tests
 - 4.1.7. Transaminases (AST, ALT) $<$ 3 times upper limit of normal values
 - 4.1.8. Creatinine clearance calculated \geq 50mL/min
 - 4.1.9. Karnofsky Performance Status Score \geq 60%.
 - 4.1.10. HLA matched 8/8 (A, B, C, DRB1) related or unrelated donor
- 4.2. **Exclusion Criteria:**
- 4.2.1. Active infection not controlled with appropriate antimicrobial therapy

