5.7.1.3 Investigational therapy: Panobinostat (PANO)

- 5.7.3.1 Patients will be treated with PANO 5 MG PO TIW (3 doses about 48 hours apart in a 7 day period) QW for 26 weeks starting prior to stem cell infusion (see Appendix G) Patient follow up will be for a total of 365 ± 30 days from initiation of the drug. During the study, PANO will be administered orally as once daily dose. Patients should receive their once-a-day oral dose of PANO approximately at the same time each day in AM or PM

(preferable PM). Each dose of PANO should be taken with about 8 oz / 240 ml glass of water. Patients should be instructed to swallow the capsules whole and not chew them. Patients must avoid grapefruit or grapefruit juice and seville (sour) oranges during the entire study.

5.7.3.2 PANO will be provided by Novartis. Oral PANO will be supplied as 5-mg pink gelatin capsules. Medication labels will comply with US legal requirements and be printed in English. They will supply no information about the patient. The storage conditions for study drug will be described on the medication label.

5.7.3.3 If the patient cannot take Panobinostat due to mucositis and/or HCT related GI toxicities (nausea/vomit/diarrhea), then he/she should take PANO on that same day within 16 hours after the missed dose if possible. After more than 16 hours, that day's dose should be withheld, and the patient should wait to take PANO until the next scheduled treatment day (i.e., patients should be instructed not to try to make-up the missed dose after 16 hours). (In our prior experience majority of patients with mucositis and/or GI toxicities were able to complete SIR PO as specified in protocol⁴).

5.7.3.4 The investigator should instruct the patient to take the study drug exactly as prescribed (promote compliance). Pill diary to help adhere with compliance is highly recommended to record actual drug compliance and will be provided to patients. All dosages prescribed and dispensed to the patient and all dose changes during the study should be recorded in pharmacy chart.

5.7.3.5 Patients will receive the planned treatment with PO PANO until they experience unacceptable toxicity that precludes further treatment (as specified in section 9).

5.7.3.6 If they develop GVHD and requires treatment with high dose corticosteroids (1-2MG/Kg) as defined in section 6 they should stop PANO as determined in section 6.3.

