To date the main adverse events reported are similar among all the studies performed with oral PANO formulations. Information about common side effects already known about the investigational drug can be found in the Investigators' Brochure (IB) or will be communicated between IB updates in the form of Investigator Notifications. This information will be included in the patient informed consent and should be discussed with the patient during the study as needed.

- 7.2.1. The most common non-hematological events (Table 1) reported were:
 - 7.2.1.1. GI events (nausea/vomiting/ diarrhea);
 - 7.2.1.2. Fatigue and electrolytes abnormalities are less common.
- 7.2.2. The most common hematological toxicity reported was thrombocytopenia and to a lesser extent mild anemia and leukopenia.

These potential adverse effects will be monitored, and their occurrence recorded as specified in section 9.2. No specific diagnostic or therapeutic measures are prescribed by this protocol for majority of toxicities unless specified. GI toxicity is a common side effect of HCT especially in the immediate transplant period (see expected HCT complications section 9). Etiology of GI symptoms could be multifactorial including conditioning

regimen, medications, GVHD and/or infections. For patients with diarrhea, evaluations for other etiologies including infection are highly recommended. Endoscopy with biopsies should be considered for evaluation of GVHD if the patient is beyond day +22, but is left to the discretion of the treating physician.

8. Reasons to hold/discontinue treatment:

- 8.1. Investigator(s) decision to withdraw patient from the study in the event of inter-recurrent illness, adverse events, or other reason that he deems necessary to discontinue study drug. Patients who discontinue from the study for AE or SAE will all be evaluable. Date of and reason for study discontinuation will be noted. Patients whose treatment is interrupted or permanently discontinued due to an AE must be followed until resolution or stabilization of the event, whichever comes first.
- 8.2. Abnormal laboratory result unable to be corrected to levels acceptable for treatment with the study drug.
- 8.3. Patient non-compliance
- 8.4. Subject withdrew consent from study at any time for any reason.
- 8.5. Death.
- 8.6. Prolongation of QTcF (see section 5.6).

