- 8.7. For patients that PANO is discontinued due to GVHD they are allowed to continue to be ON study. All assessment, procedures, CRF forms, correlative studies (appendix F) will be performed identically to patients that continue to take PANO and we will not deviate from what is stipulated in the protocol for patients that are receiving study drug on study.
- 8.8. Special considerations for toxicity observed up to day +7 post transplant: Due to unknown interactions between conditioning regimen and PANO, guidance is provided between PANO 1st dose to day +7 HCT as follows:
 - 8.8.1. PANO will be stopped for any non-hematological CTCAE (v4) grade 3 or higher toxicities unexpected for HCT (see table 8) seen between first dose of study drug and day +7 post-HCT. If there is complete reversal of toxicity, PANO can be resumed after 7 days and a minimum of one week off study drug and continued until completion of protocol-specified dosing schedule. In the absence of complete reversal of toxicity within 7 days, the study drug will be discontinued and the patient removed from the study. All such patients will remain evaluable for analysis and not replaced.

8.9. For gastrointestinal (GI) symptoms (diarrhea or nausea/vomiting) thought to be related to PANO from day -5/-6 to day +7 and/or after recovery from acute GI toxicity due to chemotherapy: The PANO dose may be modified according to the severity of the GI side effects as suggested and described in Table 6 and 7. Depending on the patients' clinical status, dose adjustments may be made within 1 week from when the lab work is completed. Patients who require PANO adjustment will have their dose HOLD for 3 doses and may resume 100% dosing thereafter at physician discretion. A trial of anti-emetics and anti-motility agents should be considered (institutional Clinical Practice Guidelines) before modifying the dose of PANO. In case patient regurgitate PANO pill will be allowed to re-dose after anti-emetics trial. PANO should continue for patients who develop GI symptoms related to infection.

Table 6. Management guidance for Diarrhea.

	Diarrhea Grade	PANO dose reduction
Mild	Grade 1: <4 stools/day over baseline	0%
Moderate	Grade 2: Increase 4-6 stools/day over baseline	0%
Severe	Grade 3: Increase >7 stools/day over baseline	No GI GVHD: hold only after failure of antimotility agents. Resume once the GI toxicity has resolved to grade 0-2 and continued until completion of protocol-specified dosing schedule If GI GVHD*

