Toxicity will be assessed using the NIH-NCI Common Terminology Criteria for Adverse Events, version(CTCAE) version 4.0 (v.4) (http://evs.nci.nih.gov/ftp1/CTCAE/CTCAE_4.03_2010-06-14_QuickReference_5x7.pdf).

9.2. AE reporting:

- 9.2.1. All non-hematological toxicities unexpected with HCT will be reported from the first day PANO is administered until day 180±7 days unless specified otherwise in the protocol. After day 180±7 post HCT subjects will only be followed only for GVHD, relapse and survival until day 365±30.
- 9.2.2. Information about relevant AE unexpected to HCT, whether volunteered by the subject, discovered by investigator questioning, or detected through physical examination, laboratory test or other means, will be collected and recorded. AE should be followed as

appropriate for at least 14 days following the last dose of PANO. All AE should be treated appropriately. Such treatment may include changes in study drug treatment including possible interruption or discontinuation, starting or stopping concomitant treatments, changes in the frequency or nature of assessments, hospitalization, or any other medically required intervention.

- 9.2.3. As far as “possible or definitive” related AE unexpected to HCT, each adverse event should be evaluated to determine:
 - 9.2.3.1. the severity grade (mild, moderate, severe) or (grade 1-4)
 - 9.2.3.2. its relationship to the study drug(s) (suspected/not suspected)
 - 9.2.3.3. its duration (start and end dates or if continuing at final exam)
 - 9.2.3.4. action taken (no action taken; study drug dosage adjusted/temporarily interrupted; study drug permanently discontinued due to this adverse event; concomitant medication taken; non-drug therapy given; hospitalization/prolonged hospitalization)
 - 9.2.3.5. whether it constitutes a serious adverse event (SAE).

- 9.3. **SAE is an undesirable sign**, symptom or medical condition which:
 - 9.3.1. Is fatal or life-threatening
 - 9.3.2. Results in persistent or significant disability/incapacity
 - 9.3.3. Constitutes a congenital anomaly/birth defect
 - 9.3.4. Is medically significant, i.e., defined as an event that jeopardizes the patient or may require medical or surgical intervention to prevent one of the outcomes listed above
 - 9.3.5. Requires inpatient hospitalization or prolongation of existing hospitalization
 - 9.3.6. Note that hospitalizations for the following reasons should not be reported as serious adverse events:

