paroxetine	Antiarrhythmics (listed below):
venlafaxine	quinidine
bupropion	lidocaine
duloxetine	mexiletine
Antiemetics (listed below):	propafenone
	Others:
	oxycodone
metoclopramide	codeine
	hydrocodone
	terbinafine
	promethazine
	tamoxifen
	Tramadol
Use of antiemetics ondansetron and dolasetron is contraindicated (granisetron use as an antiemetic is permitted).	

This is not a comprehensive list of CYP2D6 substrates. Additional updated versions of this list, which are meant to be used as a guide, may be found at the following website: <http://medicine.iupui.edu/clinpharm/DDIs> 1 Synold TW, Takimoto CH, Doroshow JH, Gandara D, Mani S, Remick SC, Mulkerin DL, Hamilton A, Sharma S, Ramanathan RK, Lenz HJ, Graham M, Longmate J, Kaufman BM, Ivy SP. Dose-Escalating and Pharmacological Study of Oxaliplatin in Adult Cancer Patients with Impaired Hepatic Function: A National Cancer Institute Organ Dysfunction Working Group Study, Clin Cancer Res. 2007 13; 3660

APPENDIX C. Study calendar for patients treated with TAC+SIR+PANO or with TAC+SIR (PANO has been discontinued due to GVHD)

Test and Procedures	Screening	-6/-5 ⁷	-1	+28	+60	+90	+120	+150	+180	+270	+365
				+/- 3days		+/- 14 days				+/- 30 days	
Medical history, complete physical exam, weight, vital signs, performance status by Karnofsky.	X			X	X	X	X	X	X	X	X
Transplant Vital organ testing. ¹	X										
BSA- Height.	X										
Consent signing	X										
TSH ⁴ , free T4 ⁴	X										X
Coagulation Profile (PT, PTT, Fibrinogen ⁴)	X										
PANO (PO) administration ⁵											
Electrocardiograms (EKGs) ²	X	X	X								
Biochemistries ³	X										
Cholesterol, LDL, HDL, triglycerides, and uric acid ⁴	X										
GVHD organ assessments				X	X	X	X	X	X	X	X
Record immune suppression				X	X	X	X	X	X	X	X
AE and SAE				X	X	X	X	X	X	X	X
Research Studies ⁶ (see Appendix F)											

¹ LVEF by MUGA and/or echocardiogram, PFT, CT chest, CT sinus, bone marrow, liver function tests, creatinine clearance, serum pregnancy test, infectious disease panel as per SOP. All must meet **inclusion criteria** detailed in body of protocol.

Exclusionary factors must be confirmed as negative upon screening evaluation, as detailed in the protocol.

² Electrocardiograms (EKGs): see section 5.6.

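### Section 8.8.1 takes patients with unresolved early toxicity off study by about day +14 but keeps them evaluable and unreplaced, without saying how they are followed or counted for the day-100 GVHD endpoint

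*Combined protocol and SAP*

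**What the plan says.** Section 8.8.1 covers non-hematological grade 3 or higher toxicity, unexpected for transplant, between the first panobinostat (PANO) dose and day +7. If it has not completely reversed within 7 days, the rule reads: "the study drug will be discontinued and the patient removed from the study. All such patients will remain evaluable for analysis and not replaced". No endpoint is named.

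Nearby text on patients who stop PANO:

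- 8.1, on adverse events: "Patients who discontinue from the study for AE or SAE will all be evaluable". Those whose treatment is interrupted or stopped "must be followed until resolution or stabilization of the event, whichever comes first".
- 8.7: "For patients that PANO is discontinued due to GVHD they are allowed to continue to be ON study", with the same assessments as patients still on drug. The Appendix C calendar title likewise names patients on the three-drug regimen and those whose PANO was stopped because of GVHD.

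General follow-up text, with no exception for removed patients:

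- 3.4: "Patients will be evaluated weekly from day of transplant until day 100 to measure acute GVHD using standard scoring system".
- 5.7.3.1: "Patient follow up will be for a total of 365 ± 30 days from initiation of the drug".
- 9.2.1: "After day 180±7 post HCT subjects will only be followed only for GVHD, relapse and survival until day 365±30".

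Statistical text:

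- 12.1 defines a patient evaluable for the primary endpoint as one who had at least one dose and neither relapsed nor died without grade II-IV acute GVHD up to day 100. Non-evaluable patients are replaced.
- 12.1 stops the trial at 7 or more events in 15. Otherwise 23 more are enrolled once 9 or more of the 15 have completed day +90 without the event. The regimen is promising at 12 or fewer events in 38.
- 12.2 makes every dosed patient evaluable for toxicity, and 12.3 makes every dosed patient eligible for the primary and secondary endpoints.
- 12.4 estimates the cumulative incidence at day 100 with death and relapse as competing risks. It states no censoring rule.

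**The concern.** A patient removed by about day +14 has most of the day-100 window still ahead. If removal ends GVHD assessment, the patient's primary-endpoint status is unknown, yet 8.8.1 keeps the patient evaluable and forbids replacement. The go/no-go rule in 12.1 is a raw count of events among 15 and then 38 patients, and a raw count has no place for an unknown: someone must score it one way or the other, or drop it.

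The reason for removal is toxicity arising during study drug, so these patients need not resemble the rest. Without a rule set in advance, the choice could be made after the results are known. Sites could also differ in practice from patient to patient, one following 8.8.1 and another 3.4.

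**Working it through.** **1. Timing.** The trigger window closes at day +7 and reversal is allowed 7 days: 7 + 7 = day +14 at the latest. The endpoint is read at day 100.

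**2. Follow-up, side by side.** 3.4, 5.7.3.1 and 9.2.1 carry all patients to day 100 or day 365. 8.8.1 takes these patients off study. 8.7 and Appendix C expressly provide continued assessment for GVHD discontinuations and are silent on toxicity discontinuations. 8.1 does not settle the point. The passages are not reconciled.

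**3. Replacement, side by side.** For a removed patient who is alive, relapse-free and followed to day 100, 8.8.1 and 12.1 agree: evaluable, not replaced. For one who relapses or dies without grade II-IV GVHD by day 100, 12.1 says replace and 8.8.1 says do not. If the patient is not followed, 12.1 cannot be applied at all.

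**4. The plan's own figures.** Inputs from 12.1: null risk 0.43, target risk 0.23, 15 patients in stage 1 (go at 6 or fewer events), 38 in total (promising at 12 or fewer). With X ~ Bin(15, p) and Y ~ Bin(23, p):

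P(promising) = sum over x = 0 to 6 of P(X = x) × P(Y ≤ 12 − x).

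This gives 0.0958 at p = 0.43 and 0.9038 at p = 0.23. A full search returns the same design as minimax for 10% and 10% error. Only 0.4 percentage points lie between 9.6% and the 10% limit.

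**5. Unassessed patients in the count.** Let k1 and k2 be the numbers unassessed in stages 1 and 2, so that X ~ Bin(15 − k1, p) and Y ~ Bin(23 − k2, p). Scored GVHD-free, the conditions are X ≤ 6 and X + Y ≤ 12. Scored as events, they are X + k1 ≤ 6 and X + Y + k1 + k2 ≤ 12. The documents give no removal rate, so one or two patients is an assumption.

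| k1, k2 | Scored GVHD-free: type I error at 0.43 | Scored as events: power at 0.23 |
|---|---|---|
| 0, 0 | 0.0958 | 0.9038 |
| 0, 1 | 0.1178 | 0.8639 |
| 1, 0 | 0.1215 | 0.8383 |
| 0, 2 | 0.1434 | 0.8050 |
| 1, 1 | 0.1486 | 0.7859 |
| 2, 0 | 0.1523 | 0.7382 |

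If the patient is instead followed to day 100, or is excluded and replaced, the first row holds; replacement costs accrual.

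**6. Stage 1.** Fewer than 7 events and at least 9 event-free completers are the same condition only when all 15 are assessed. With one unassessed, 6 events and 8 completers meet neither wording. The probability is that of exactly 6 events in 14, 3003 × p^6 × (1 − p)^8: 0.2115 at 0.43 and 0.0549 at 0.23. This presupposes a removal in stage 1. If a single removal is equally likely at any of the 38 places, that chance is 15/38 = 0.395, which brings the figures to about 8% and 2%, still given that a removal occurs.

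**The case against.** The best defence is that 8.8.1 sits in a section about holding or stopping treatment, so removal may mean off drug only, with 3.4, 5.7.3.1 and 9.2.1 continuing to apply. That reading is possible, but the text does not state it. 8.8.1 lists stopping the drug and leaving the study as two consequences, and 8.7, just before it, distinguishes being off drug from being off study. Evaluability could also mean for toxicity only, under 12.2. Again the text does not say so, 12.3 admits dosed patients to the primary endpoint, and the only other replacement rule is the one for the primary endpoint in 12.1.

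Several stronger readings are tempting and are not supported:

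- A reader might infer that 8.1 ends follow-up when the adverse event resolves. It sets a minimum for adverse-event follow-up. It also covers patients whose treatment is merely interrupted, who plainly stay on study.
- A reader might infer that the plan requires unassessed patients to be counted as GVHD-free. It does not. Under 12.1 a patient with unknown day-100 status cannot be shown to be evaluable, so exclusion with replacement is as literal a reading, and it leaves type I error at 9.6%.
- A reader might infer that the cumulative-incidence estimate is distorted in the same way. The 12.4 method would ordinarily censor a lost patient. The difficulty lies in the 12.1 count.
- A reader might infer that stage 1 can always deadlock. The completion of 9 patients can be read as a timing trigger, with fewer than 7 events as the go condition; then there is no gap.
- The onset range of day 26 to 100 in section 1.4 comes from a trial that enrolled patients who already had GVHD. It is context, not evidence of when GVHD would appear here.

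It also stands that few patients may be affected: Table 8 classes most transplant toxicities as expected, and 8.8.1 further needs grade 3 or higher, an early window and non-reversal.

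**Conclusion.** The point holds as a failure to reconcile sections, and it is worth fixing. 8.8.1 as written conflicts with the general follow-up text, contradicts 12.1 on replacement for patients who relapse or die without GVHD by day 100, and leaves patients with unknown day-100 status without a counting rule.

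The size is conditional. The shifts from one patient (about 2 percentage points or slightly more in type I error, or 4 to 6.5 points in power) rest on an assumed removal, on that patient not being followed, on one particular scoring in the 12.1 count, and on all other patients having the stated risk. The stage-1 gap further needs the removal to fall among the first 15 and the completion wording to be a go condition. The design itself is sound when every counted patient has a known day-100 status.

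**What to change.** Leave the toxicity and dosing rules as they are, and change four pieces of text:

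1. In 8.8.1 and 8.1, state that these patients leave study drug only. GVHD assessment continues to day 100, and GVHD, relapse and survival follow-up to day 365, as 8.7 already arranges for GVHD discontinuations.
2. Extend the Appendix C title to match.
3. Reconcile the no-replacement statement in 8.8.1 with 12.1, so that one rule covers patients who relapse or die without GVHD by day 100.
4. Before data are seen, set one counting rule, used at both the 15- and 38-patient looks, for anyone whose day-100 status is still unknown, for example after consent is withdrawn. The choice is the sponsor's. Scoring unknowns as events costs power, scoring them GVHD-free costs type I error, and replacing them costs accrual.

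The cost is protocol wording plus some extra follow-up and CRF pages for probably few patients. Items 1 and 2 should make unknowns rare, so the choice in item 4 should seldom matter.

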Safety assessments will consist of monitoring and recording focused toxicities/adverse events (AE) and serious adverse events (SAE) unexpected to HCT (table 8), the regular monitoring of hematology, blood chemistry and urine values, vital signs, ECOG/Karnofsky performance status, and the regular physical examinations and EKG assessments as specified in the protocol.

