9.1. AE definition: An adverse event (AE) is the appearance or worsening of any undesirable sign, symptom, or medical condition occurring after starting PANO that is unexpected with HCT. Table 8 describes criteria for “expected” toxicities for HCT/GVHD-related symptoms that are commonly observed in transplant patients. Certain Grade 4 toxicities under particular categories in the NCI CTCAE are common in the HCT transplant setting, and patients with Grade III or IV GVHD are likely to experience additional serious symptoms. These listed toxicities are likely related either to the HCT or preparatory and treatment regimens, however, the investigator must use best medical judgment in making an assessment as whether or not the study drug (PANO) may have had a contributory role.

Table 8. Expected Transplant/GVHD-Related Toxicities in HSC Transplant Patients.

Category	Symptoms/Event	Category	Symptom/Event
Dermatological	Pruritus Rash/dermatitis associated with high-dose chemotherapy or GVHD	Renal/Genitourinary	Bladder spasms/cystitis Creatinine elevation/renal failure Dysuria frequency-urgency Urinary retention
Constitutional	Fever, Rigors, Chills Headache Tremors Weight lost and gain Confusion due to medications Peripheral edema	Reproductive	Persistent amenorrhea
Gastrointestinal	Gastritis GERD Colitis Dehydration Diarrhea Nausea/vomiting Dysphagia Stomatitis/pharyngitis Hematocheza/melena Abdominal pain or cramping	Metabolic/Laboratory	Acidosis/alkalosis Amylase/lipase elevation Hypo-/Hyperglycemia Hypo-/Hyperkalemia Hypo-/hypercalcemia Hypo-/Hypermagnesium, Hypophosphatemia Hypo-/Hypernatremia Hypertriglyceridemia/Hyperlipidemia/hypercholesterolemia Hyperuricemia Increased LDH

Category	Symptoms/Event	Category	Symptom/Event
Hepatic	LFT elevation Bilirubin elevation Hypoalbuminemia Hepatomegaly	BMTComplex/ Multicomponent Events	GVHD* Stem-cell infusion complications Venoocclusive Disease/ascites
Cardio-vascular	Edema Hypertension/Hypotension Sinus tachycardia Arrhythmia (Atrial fibrillation/flutter; Sinus ventricular tachycardia and others) Vascular access complication- deep vein thrombosis requiring anticoagulation Thomboembolic event	Hematologic	Cytopenias Catheter associated venous thrombosis
Infections*	Bacterial, fungal and/or viral infections Sepsis/confusion		

*Infection and GVHD: These toxicities will not be considered AEs but data will be captured on eCRFs. Other toxicities will NOT be captured as expected HCT complications.

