11.7. Instructions for data reporting

- 11.7.1. To ensure patient safety, every SAE, regardless of suspected causality, occurring after the patient has provided informed consent and until at least 14 days after the patient has stopped study treatment must be reported to Novartis within 24 hours of learning of its occurrence.

Any SAEs experienced after this 14 days period should only be reported to Novartis if the investigator suspects a causal relationship to the study treatment. Recurrent episodes, complications, or progression of the initial SAE must be

reported as follow-up to the original episode within 24 hours of the investigator receiving the follow-up information. An SAE occurring at a different time interval or otherwise considered completely unrelated to a previously reported one should be reported separately as a new event.

Information about all SAEs is collected and recorded on the Serious Adverse Event Report Form as outlined per contractual agreement; all applicable sections of the form must be completed in order to provide a clinically thorough report. The investigator must assess and record the relationship of each SAE to each specific study treatment (if there is more than one study treatment), complete the SAE Report Form in English, and send the completed, signed form by fax within 24 hours to the oncology Novartis Drug Safety and Epidemiology (DS&E) department.

The telephone and telefax number of the contact persons in the local department of Drug Safety and Epidemiology (DS&E) are included in the contractual agreement. The original copy of the SAE Report Form and the fax confirmation sheet should be kept with the case report form documentation at the study site.

Follow-up information is sent to the same contact(s) to whom the original SAE Report Form was sent, using a new SAE Report Form stating that this is a follow-up to the previously reported SAE and giving the date of the original report. Each re-occurrence, complication, or progression of the original event should be reported as a follow-up to that event regardless of when it occurs. The follow-up information should describe whether the event has resolved or continues, if and how it was treated, whether the blind was broken or not, and whether the patient continued or withdrew from study participation.

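### Serious transplant-expected events fall under two conflicting recording rules, and late GI toxicity that section 9.4 attributes to panobinostat may not count in the section 12.2 stopping rule

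*Combined protocol and SAP*

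**What the plan says.** **The filter.** Section 9.1 defines an adverse event as one "occurring after starting PANO that is unexpected with HCT". Table 8 then lists what counts as expected, including diarrhea, nausea/vomiting, cytopenias, liver test elevation, veno-occlusive disease, arrhythmia and thromboembolic events. For infection and GVHD its footnote says "These toxicities will not be considered AEs but data will be captured on eCRFs"; for the rest, "Other toxicities will NOT be captured as expected HCT complications". Section 7 describes safety recording as covering focused toxicities and "serious adverse events (SAE) unexpected to HCT (table 8", so there the filter reaches serious events. Section 9.2.1 reports only non-hematological toxicity that is unexpected with transplant.

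**No filter.** Section 9.3 defines an SAE by its consequences, for example "Requires inpatient hospitalization or prolongation of existing hospitalization". Its exclusions (9.3.6) cover only routine, elective or social admissions and emergency outpatient care. Section 9.3.7 refers to section 11.7, where 11.7.1 requires 24-hour reporting to the drug supplier of "every SAE, regardless of suspected causality, occurring after the patient has provided informed consent".

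**Attribution and stopping.** For Table 8 events, section 9.1 asks the investigator to judge "whether or not the study drug (PANO) may have had a contributory role". Section 9.2.3 opens with events already thought possibly or definitely related: "related AE unexpected to HCT, each adverse event should be evaluated to determine" severity, relationship, duration, action and seriousness. Section 9.4 treats grade 3-4 diarrhea and vomiting after day +22, with infection and GVHD excluded, as probably or definitely related to panobinostat, and says section 12.2 contains stopping rules for excess GI toxicity. Section 12.2 and the notes to Table 9 count patients with grade 3 or higher toxicity unexpected with transplant.

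**The concern.** The same clinical event can be outside recording under one section and reportable within a day under another. In a single-arm trial no concurrent randomized group would reveal an excess that was not written down, so the SAE record carries much of the safety information.

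The stopping rule has a related problem. Section 9.4 picks out two late GI toxicities as the drug's own and says the stopping rule deals with them. If those events stay expected because Table 8 lists them, the rule does not see them. Section 9.2.3 adds a circularity: it asks for grade and relationship only once relatedness has been presumed.

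**Working it through.** The main check sets the sections against one another. The one related figure in the plan is reproduced first.

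**1. The plan's stopping probabilities.** Section 12.2 gives 4.9%, 79% and 98% at true rates of 20%, 40% and 50%. The rebuilt boundary takes, at each n, the smallest c with P(X ≥ c | n, 0.20) ≤ a, with a set so that overall stopping at a 20% rate is at most 5%. With 38 patients (the evaluable number in section 12.1), a is about 0.0162 and exact recursion gives 4.9%, 79.1% and 97.7%. With 44 patients it gives 4.9%, 83.1% and 98.7%, so the printed figures fit 38. Two limits apply: the columns for n = 13-20 and n > 30 are not in the available text and were filled by the same rule, and the printed cell at n = 12 is 6 where the calculation gives 7. The figures hold for whatever rate of events is counted. They do not say which events those are.

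**2. A serious Table 8 event, taking life-threatening veno-occlusive disease as the example.**
- Section 9.1: not an AE, because it is listed as expected.
- Table 8 footnote: not captured, because it is neither infection nor GVHD. The footnote does not mention seriousness.
- Section 7: outside the SAEs to be recorded, because it is not unexpected.
- Section 9.3: an SAE, because it is life-threatening.
- Sections 9.3.7 and 11.7.1: reportable within 24 hours.
- Section 10.12.3: findings that meet the AE and SAE definitions must be recorded, without saying whether section 7's limit applies.

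No section ranks these rules. Arrhythmia and thromboembolism follow the same path when serious.

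**3. Grade 3 diarrhea after day +22, infection and GVHD excluded.**
- Section 9.4.1.2: an AE, probably or definitely related to panobinostat, and said to be covered by section 12.2.
- Table 8: listed, hence expected.
- Section 12.2: a single boundary, for unexpected grade 3 or higher toxicity. It has no separate GI boundary.

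Read literally, the event does not count. Vomiting (9.4.2.2) follows the same path. A hypothetical case shows that a decision can turn on this. Table 9 suspends accrual at c = 6 for n = 10. Suppose 5 of 10 patients have unexpected grade 3 or higher toxicity and one other patient has only the section 9.4 diarrhea. The literal count is 5 and accrual continues. With the section 9.4 event, 5 + 1 = 6 and accrual is suspended.

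**4. Other known panobinostat effects.** Section 7.2 names GI events and thrombocytopenia as the most common and promises recording through section 9.2. Section 9.2.1 leaves out hematological toxicity and anything expected, so that route does not deliver what section 7.2 promises.

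**The case against.** The operative chain for serious events is explicit. Section 9.3 does not use the filtered AE term, 9.3.7 points to 11.7, 11.7.1 covers every SAE, and section 11 repeats that SAE reporting to the supplier is required. The reach to serious events rests on an introductory clause in section 7. This stands in part: staff who follow 9.3.7 to 11.7.1 would report these events, so loss is possible but not directed. There is one centre, so sites cannot diverge, though staff still have two instructions.

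The footnote can also be read narrowly: listed events are not captured as transplant complications, which leaves those attributed to panobinostat capturable. Sections 9.1 and 9.4 support that reading. It is reasonable, but the text does not state it, and it does not bring the section 9.4 events into a rule confined to unexpected toxicity.

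A reader might infer that the dataset cannot show panobinostat toxicity. The documents do not support that. Fatigue and QTcF prolongation are not named in Table 8. Cytopenias trigger dose holds (8.11-8.12), and administered doses are recorded (10.12.2). Infection and GVHD go on eCRFs. Engraftment and non-relapse mortality are endpoints, so fatal cases would appear as deaths.

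The background rates do not measure the loss either. Diarrhea at 61.0%, nausea at 55.9% and thrombocytopenia at 53.9% (Table 1 of section 1.5) are pooled over 20-60 mg, whereas this trial uses 5 mg. Grade 3-4 thrombocytopenia alone ranges from 21.4% at 20 mg to 79.1% at 40 mg (Table 2 of section 1.5).

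Finally, not recording routine, non-serious transplant morbidity is a legitimate choice. Wider eCRF capture of such events is a trade-off for the investigators and is not pressed here.

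**Conclusion.** The point holds as two textual conflicts and one drafting fault. First, a serious Table 8 event falls under incompatible rules and may go unrecorded. Second, the grade 3-4 diarrhea and vomiting that section 9.4 attributes to panobinostat would not, read literally, count in the stopping rule that section 9.4 invokes. Third, section 9.2.3 puts relatedness ahead of grading.

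No rate can be attached, because the documents give neither the share of serious events that are Table 8 events nor the expected number of section 9.4 events. A reader might shrink the 40% toxicity rate by some share of events not called related and conclude that the 79% stopping probability collapses. That does not follow. Section 12.2 counts unexpected grade 3 or higher toxicity whatever its cause, so relatedness does not enter the rule. Its 20% and 40% are already rates of unexpected toxicity, and any such share would be invented.

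The conclusion rests on the plain wording and assumes that no other trial document, such as the contract or eCRF instructions, already settles which rule prevails.

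**What to change.** - In section 7, section 9.1 and the Table 8 footnote, state that the exclusion of expected events applies to non-serious events only, and that every event meeting section 9.3 is recorded and reported under section 11.7.1.
- Reconcile section 9.4, Table 8 and section 12.2 so that it is explicit whether the diarrhea and vomiting attributed to panobinostat are captured as AEs and counted in c. If they are, confirm that the 20% reference rate is meant to include them.
- Reword section 9.2.3 so that each reportable AE is graded first and its relationship judged afterwards.
- Align the recording promise in section 7.2 with the scope of section 9.2.1.

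These are protocol wording changes that alter no dose or treatment rule. The cost is an amendment and slightly more SAE and AE data entry.
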